“Harvest for Health” is a home-based vegetable gardening intervention that pairs cancer survivors with certified master gardeners (MGs) from the Cooperative Extension System, the education and outreach arm of land-grant universities nationwide.¹⁻⁵ Preliminary results suggest that this intervention increases vegetable consumption and physical activity, and improves physical functioning and health-related quality of life (hrQoL).¹⁻³ The “Harvest for Health” program has tremendous potential for sustainability, and widespread dissemination and implementation since MG programs exist in all 50 United States.^{6,7} To date, it has been tested in primarily non-Hispanic white cancer survivors living in Alabama. We propose a pilot study to adapt this promising program to the multi-cultural population of cancer survivors and for the local context (physical, social, and cultural environment) of New Mexico. We will then implement the adapted program, “Southwest Harvest for Health”, and evaluate the feasibility and acceptability through a pilot study taking place in Bernalillo and Southern Sandoval Counties in New Mexico. Our transdisciplinary research team is well-poised to pursue the following specific aims:

Aim 1: Adapt the “Harvest for Health” intervention to the drastically different climate and growing conditions, and the multi-cultural population of New Mexico using a recommended adaptation framework.^{8,9}

Aim 2: Assess the feasibility and acceptability of the “Southwest Harvest for Health” program through recruitment and retention rates, adherence/fidelity to the intervention, and acceptability of the program for both cancer survivors (participants) and Cooperative Extension Master Gardeners (volunteer mentors). We hypothesize that we will be able to

PROTOCOL TITLE: Southwest Harvest for Health Pilot

recruit 25-30 cancer survivor / MG dyads (based on similar geographic location) within 6 months, retain >80% of the sample, and achieve 80% adherence/fidelity to the protocol and intervention. We also hypothesize that we will receive positive feedback on the mentored vegetable gardening program from both participants and MGs.

Aim 3: Obtain estimates on pre-post changes in secondary endpoints including vegetable servings per day, physical activity, sleep quality, physical functioning and performance, and hrQoL.

Aim 4: Conduct a process evaluation using qualitative and quantitative measures to inform a larger definitive trial

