Cancer survivors interested in participating will contact a member of the Southwest Harvest for Health (SWH4H) study team. The screening will take place by telephone. The study coordinator/recruiter will provide additional information about the study, answer questions and assess eligibility using the study recruitment script.

Inclusion Criteria

Twenty-five adult (50 years and older) male and female cancer survivors residing within Bernalillo and southern Sandoval County will be recruited for this study. Additional eligibility criteria include:

- Diagnosed with an invasive, non-metastatic cancer; metastatic cancer patients are eligible with MD written or verbal approval
- Completed primary treatment (surgery, radiation, chemotherapy); note that endocrine therapy is allowed.
- Able to read, speak, and understand English. (The future larger trial will include Spanish-Speaking participants)

PROTOCOL TITLE: Southwest Harvest for Health Pilot

- Not told by a physician to limit physical activity and no pre-existing medical condition(s) that would preclude gardening, e.g., severe orthopedic conditions, hip or knee replacement surgery within 6 months), end-stage renal disease, paralysis, dementia, blindness, unstable angina, untreated stage 3 hypertension, or recent history of myocardial infarction, congestive heart failure, or pulmonary conditions that required oxygen or hospitalization within 6 months.
- Community dwelling and not residing in a skilled nursing or assisted living facility (must be able to tend to their garden and cook their own meals).
- Residing within 30 miles of one of the Master Gardener volunteer mentors
- Currently not adhering to the recommended number of fruit and vegetable servings per day (consuming fewer than 5 servings of vegetables and fruits/day and not meeting the recommended guidelines for moderate-to-vigorous physical activity (< 150 minutes/week)
- Reside in a location that can accommodate a 4' x 8' raised garden bed or 4 (29" x 14") garden containers, or adequate (at least 4 hours) of sunlight per day and have access to running water
- No existing or recent (within the past year) experience with vegetable gardening
- Able to participate in the 10-month intervention (all three seasonal gardens; roughly from mid-February through early November 2020)

Exclusion Criteria

Individuals will be excluded from participation if they:

- Are not able to consent

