- Are not competent due to mental health or other very serious comorbid conditions (e.g., stroke, degenerative neurological conditions)
- Have any medical condition that substantially limits daily light-intensity physical activity (i.e. activities of daily living: bending, stooping, walking, etc.)

Also excluded from participation in the proposed study:

- Due to the focus on older cancer survivors, individuals who are not yet adults (infants, children, teenagers) or who are considered adolescent and young adults (ages 15-39) will be excluded from this study. In the future, this study may be adapted to suit adolescent and younger cancer survivors.
- Given the focus on older (50+ years) cancer survivors, women who are pregnant or who are planning to become pregnant, will be excluded from this study.
- Prisoners may not participate in this study as this is a home-based gardening intervention and we are seeking participants who are able to pursue lifestyle changes independently and not as the result of institutional control

Note: Verification of adequate space, sunlight, and running water to support a vegetable garden will occur at the baseline home visit. If these criteria are not met, then the individual

PROTOCOL TITLE: Southwest Harvest for Health Pilot

is not eligible to participate and will receive a \$20 merchandise card for their time. Note that this assessment will take place before any further collection of data.

4. Number of Subjects

The proposed study will enroll 25 to 30 cancer survivors. This study has proved to be very popular, and with multiple recruiters, we reached our original accrual goal of 25, and now have a waitlist. We would like to allow an additional 5 participants (30 maximum).

5. Study Timelines

The proposed grant period is two years with the actual intervention being 10 months (plus or minus 14 days due to scheduling difficulties). Recruitment will occur over a four month period, beginning November 2019. Enrollment of 25-30 participants will be completed by late February/early March 2020. All participants are expected to begin the intervention at the same time (plus or minus 10 days to account for weather and/or scheduling conflicts between the Master Gardener and the participant). The proposed intervention is expected to begin in early March 2020 and end in mid-November 2020, coincident with three gardening seasons (spring, summer, and fall). Data analyses will be completed before March 2021.

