- obtaining the voluntary informed consent of individuals to be subjects in research; and
- studying, interpreting, or analyzing identifiable private information or data for research purposes.”

Based on this definition of investigators, the MG volunteers are not research investigators. MGs will be performing their regular activities, which include disseminating their horticultural knowledge to the general public via volunteer opportunities. Southwest Harvest for Health will be offered as a volunteer opportunity for certified MGs from Bernalillo and Sandoval counties for 2020.

Time Devoted to Conduct the Research

This is a two-year study. Within the first six months, we will finalize study materials and identify potentially eligible cancer survivors. Data cleaning and preparation for analyses will be ongoing. Analyses will be conducted and manuscripts prepared during the last two months of the study.

Study Timeline: August 2019 – July 2021																		
Month	2019				2020										2021			
	A -	N -	J	F	M	A	M	J	J	A	S	O	N	D	J	M	M	J
Development																		
Recruitment																		
Intervention delivery																		
Data cleaning/prep																		
Analyses																		
Publications										1						2		
Grant Submissions														3				4

¹ Study protocol

² Study outcomes

³ Initial R01 submission

⁴ Revised R01 submission

PROTOCOL TITLE: Southwest Harvest for Health Pilot

8.1. Describe other resources available to conduct the research:

This is a small feasibility study (25-30 Cancer Survivors) with broad eligibility criteria (e.g., 50 years and older, any local or regionally staged cancer type, etc.); therefore, we do not anticipate having difficulty recruiting for this study. Additionally, the study design seeks to reduce participant burden by providing a home-based intervention, i.e., a vegetable garden at their home and home visits to assess study outcomes. Also, the study is designed for sustainability as the participants will keep the study provided gardening supplies.

Facilities where Research will be conducted

This is a home-based study. The intervention and assessment of health, health behaviors and physical function will take place by trained investigators in the participant's home. Recruitment and screening will take place in a private office in the UNM's Cancer Research Facility. Data management and data analyses will also take place in the UNM's Cancer Research Facility.

COVID-19 Modification

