The screening/recruitment and study questionnaire data will be directly entered onto a data collection form in REDCap, a secure UNM Data Security approved system. Access to the study REDCap database will be limited to specific study staff users at the discretion of the study Principal Investigator (PI), [name], and in accordance with institutional review board policies. Data generated during the course of the study will be managed in compliance with the general guidelines for the Use of Confidential Data used by our IRB. Unique identification numbers will replace all names whenever a name is not essential for research purposes and will be kept separate from subject identifiers, except in the case of a password protected subject master file created by the PI approved study staff member. Electronic access to all personally identifiable data will be kept to the minimum necessary to accomplish the project and will require approved access to the REDCap database (i.e., projects). All copies of files containing personally identifiable data will be stored in separate, locked cabinets in rooms where unauthorized persons do not have access. All personnel will be trained in appropriate security measures for handling personally identifiable data they will not disclose any such information to any person or agency.

The following steps will be taken to maintain confidentiality:

- Telephone calls will take place in closed door offices or cubicles in the CRF to ensure privacy.
- Study participants will be assigned a unique study ID.
- All data collected will be identified with the unique study ID.
- Identifying information (e.g., name, address, etc.) will be kept separate from the participant's study data.

PROTOCOL TITLE: Southwest Harvest for Health Pilot

- Only trained staff will have access to the data.
- Data collected during the study will be stored on a password and firewall protected server and accessed via secured computers in the Cancer Research Facility (CRF). Any paper forms, including informed consent forms will be kept in a locked file cabinet in locked offices of the study staff for up to 4 years after completion of the study.
- Study staff are required to have completed training for the responsible conduct of research.

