Recruitment will begin in November of 2019. We aim to recruit 25-30 participants to this study via passive recruitment methods. Recruitment flyers will be distributed in community locations such as libraries, grocery stores, community centers, senior centers, and cancer survivor groups. Additionally, oncologists or physicians may refer their patients (cancer survivors) to the study by giving them a study flyer. Faculty and staff from the Division of Epidemiology, Biostatistics, and Preventive Medicine and the UNM Comprehensive Cancer Center will be emailed a copy of the study flyer, provided approval from leadership (i.e., Division Chief, Associate Directors or Program Leaders). The email will briefly explain the study, and indicate a \$5 gift card for one of UNM HSC campus coffee shops will be provided for anyone referring an individual to the study, regardless of final eligibility (referred individual must contact study staff). Upon being contacted, a member of the study team will use a recruitment script to determine level of interest in the study, answer questions and assess eligibility; only trained members of the study team will screen, consent and enroll participants into the study.

20. Provisions to Protect the Privacy Interests of Subjects

The following steps will be taken to secure the data and to maintain participants' privacy:

PROTOCOL TITLE: Southwest Harvest for Health Pilot

Maintaining privacy during recruitment

The recruitment screening process will take place over the phone in a private room. Participants not eligible to participate in the study will be asked if they would like to be added to the future contact database (UNM HRPO IRB Protocol Number 18-629) in order to be made aware of future studies. If their answer is “no” all information about the ineligible participant will be destroyed. If “yes”, their contact information will be added to the secure future contact database and the paper form of the recruitment screener will be held in a locked cabinet indefinitely.

Maintaining privacy during collection of data for study outcomes

Data collection will occur at the participant’s home by trained members of the study team. Note that the Master Gardeners do not collect any data from the study participants.

Maintaining privacy during intervention delivery

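### Does destroying the records of ineligible callers who decline future contact undermine the recruitment results?

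*Combined protocol and SAP*

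**What the plan says.** Section 20, under the paragraph on privacy during recruitment, deals with people screened by telephone. Those found ineligible are asked whether they wish to be listed for later studies. If they refuse, "all information about the ineligible participant will be destroyed". If they agree, their contact details go to a separate secure database and "the paper form of the recruitment screener will be held in a locked cabinet indefinitely".

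Section 15 describes data handling in general. "The screening/recruitment and study questionnaire data will be directly entered onto a data collection form in REDCap", and "Unique identification numbers will replace all names whenever a name is not essential for research purposes". The same section provides for paper forms to be locked away for up to four years. It does not say what is kept for ineligible callers.

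Aim 2 and Section 6 assess feasibility "through recruitment and retention rates, adherence/fidelity to the intervention, and acceptability of the program". The numerical recruitment target is 25 to 30 dyads within six months in Aim 2, and 25 to 30 survivors during four months in Section 12.1. Section 12.1 relies on detailed process data to assess accrual and plans no formal test. No section names a screening log, a screened denominator or a table of exclusion reasons.

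Three remarks bear on the larger trial. Section 3 says, on language, "The future larger trial will include Spanish-Speaking participants" and, on age, "In the future, this study may be adapted to suit adolescent and younger cancer survivors". Section 8.1 describes a study "with broad eligibility criteria (e.g., 50 years and older, any local or regionally staged cancer type, etc".) and expects no difficulty in recruiting.

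**The concern.** A pilot is often the best source of information on how many people must be screened to enrol one participant, and on which criteria turn people away. Taken literally, the rule in Section 20 removes from the record every ineligible caller who does not want to be contacted again. The exclusion reasons that survive would then come only from people willing to be recontacted, a self-selected group, and the count of people screened would be short.

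The protocol gives reasons to want this information. It foresees a larger trial with Spanish-speaking participants and possibly a version for younger survivors, and it calls its criteria broad although Section 3 lists ten bulleted requirements beyond age and county. Ineligible callers were clearly expected, since the referral gift card is payable whatever the caller's eligibility. If recruitment rate were read as enrolled divided by screened, an endpoint of the study would be affected.

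**Working it through.** The plan states no screening yield, screened number or exclusion rate, so there is no figure to reproduce. The check is whether any stated result needs the records that may be lost, and what could be said about a summary that does.

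**Stated results.**

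- Recruitment: the inputs are the number enrolled and the length of the recruitment period. The target as a rate is 25/6 = 4.2 to 30/6 = 5.0 per month on Aim 2's six months, or 25/4 = 6.25 to 30/4 = 7.5 per month on Section 12.1's four months. The number screened appears in neither.
- Retention: participants retained divided by participants enrolled, against 80%. No screening records are used.
- Adherence and fidelity: contacts and logs among enrolled dyads, against 80%. No screening records are used.
- Pre-post changes: data from enrolled participants only.

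Section 4 records that the original goal of 25 was reached and that there was a waitlist, which can be established without any record of ineligible callers.

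**A screened-to-enrolled summary, if the team chose to report one.** Let E be the number enrolled, S the surviving screening records and k the records destroyed. The apparent yield is E/S and the true yield is E/(S + k). With assumed values E = 30 and S = 50:

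- k = 0: 30/50 = 60.0%
- k = 1: 30/51 = 58.8%
- k = 5: 30/55 = 54.5%
- k = 10: 30/60 = 50.0%

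Only E = 30 has a basis in the documents, as the maximum enrolment. S and k are invented to show the mechanism, so these percentages are not an estimate of any error in this study.

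**Direction of error.** Let e be the number of eligible callers and i the number of ineligible callers. Suppose a share r of the eligible records and a share d of the ineligible records are not kept. The apparent eligible proportion is e(1 − r) / [e(1 − r) + i(1 − d)], against a true value of e/(e + i). It is too high when r < d, correct when r = d and too low when r > d. Section 20 bears on d. The plan is silent on r, that is, on callers who were eligible but lost interest or never returned the consent form described in Section 24. The direction for eligible/screened is therefore not fixed by the documents. If r is above zero, enrolled/eligible would also be overstated. Enrolled/screened can only be overstated, provided every enrolled person's record is kept.

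**Sections 15 and 20 side by side.** One speaks of direct entry in REDCap and the other of a paper screener. Section 15 itself provides for paper forms, so the two can coexist and there is no contradiction to resolve.

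**People who fail at the baseline visit.** The destruction rule follows a sentence about telephone screening. Under Section 24 the baseline visit is scheduled only after signed consent and enrolment. Section 15 keeps consent forms for up to four years, and Section 3 gives a merchandise card to anyone found ineligible at that visit. The text does not settle the point outright, but it points away from the rule reaching these people.

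**The case for a change.** The best case for a change is that the sentence in Section 20 is unqualified, that no other section rescues a count, and that the remedy would cost almost nothing: one anonymous entry per caller, giving eligibility and main reason, with no added contact or questions. Recruitment rates are a named feasibility measure, Aim 4 is a process evaluation meant to inform a larger trial, and a good pilot report shows how many people were screened and why they were excluded.

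Much of this stands. The literal reading is available, no exemption for a tally is written down, and an anonymous tally would be good practice. What does not stand is the step from there to a fault in the plan. In a privacy paragraph, information about a person most naturally means that person's own record, and a count of ineligible calls need not be covered. Section 12.1's detailed process data could include such a count, as could the recruitment script and operating procedures, which are not in the documents.

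The value to the larger trial is also limited. Recruitment was passive, by flyer and self-initiated call, so callers turned away for language or age would not measure demand among Spanish-speaking or younger survivors even if every one were counted. Inclusion of Spanish speakers in the larger trial is already stated as decided.

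**Conclusion.** No change to the plan is called for. This is a missing detail about an optional summary, and analysts can handle it sensibly when they report. Followed as written, the plan still gives sound answers on accrual, retention, adherence and pre-post change, because none of these uses the records of ineligible callers. What could be incomplete is a screened count and a list of exclusion reasons that no section defines as an endpoint. The amount is unknown and possibly zero: it is zero if no ineligible caller declined recontact, or if an anonymous tally was kept.

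There would also be little gain now. The original accrual goal had been met with a waitlist, and Section 11 records that the study launched in March 2020, so new wording could not recover anything already destroyed. If the team reports a screening flow, it would report what it holds and say whether the screened count and reasons are complete.

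The conclusion rests on reading recruitment success as the count over time that Aim 2 and Section 12.1 state. It would need another look only if the sponsor intended a formal screened-to-enrolled criterion, and nothing in the documents suggests one.
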